#### 3.3.5.4 Assignment of Dates of Disease Progression or Disease Response

For all analyses of endpoints resulting from an application of modified RECIST 1.1 (dose escalation phase), RECIST 1.1 (expansion phase) to investigator assessed tumor measurements, and irRECIST, there may be cases in which disease assessments span a series of dates. For establishing the start date of a subsequently confirmed response in which the disease assessment spans multiple days, the response date assigned will be the latest date of evaluations corresponding to the disease assessment. The date of latest assessment will also be assigned for a mid-study assessment showing SD as the date assigned for the purposes of censoring of duration of response, TTP and PFS.

The date of PD will be the first date at which any objective diagnostic test provides data indicating PD. Specifically, the date of PD will be the earliest of the following 3 dates:

- Date of PD as indicated by target lesions: If PD is triggered by a change in sum of diameters of target lesions, and the dates of evaluation of the target lesions vary for the same assessment, assign the first evaluation date among target lesions.
- Date of PD as indicated by non-target lesions: If the dates of evaluation of the non-target lesions vary for the same assessment, assign the first evaluation date for which any non-target lesion exhibits a status of Unequivocal Progression.
- Date of PD as indicated by new lesions: If multiple new lesions are identified and the dates of evaluation for the new lesions vary for the same assessment, assign the first evaluation date for which any new lesion is detected.

## 3.5 Patient Reported Outcomes

All statistics listed in this section will be summarized for the As-treated Population. An additional summary may be presented for the Re-treated Population.

#### 3.5.1 Pain Questionnaire

Pain scores were planned as per protocol early in this trial but were removed during the dose escalation phase in Protocol Amendment 3. Pain scores will be listed.

## 3.6 Pharmacodynamic Endpoints and Analyses

## 3.6.1.1 Pharmacodynamic Endpoints

Exploratory pharmacodynamic endpoints are listed in the protocol.

#### 3.6.1.2 Analysis of Pharmacodynamic Endpoints

The pharmacodynamic endpoints will be analyzed by the MedImmune Translational Sciences group or designee.

## 3.7 Other Additional Analyses

Not applicable.

## 3.8 Safety Analyses

All statistics listed in this section will be summarized for the As-treated Population. An additional summary may be presented for the Re-treated Population. If the number of subjects in the Re-treated Population with available data is less than 5% of the total number of subjects in the As-treated Population for overall summary (across disease types) or < 5 subjects for one disease type at one scheduled time of evaluation, no summary statistics will be presented at that time point for overall summary or for that disease type, unless otherwise indicated.

#### 3.8.1 Maximum Tolerated Dose

The Maximum Tolerated Dose (MTD) will be based on the DLT Evaluable Population. In summary, the number and percentage of subjects with a DLT during the Dose Escalation Phase will be presented by treatment groups. The MTD level will be indicated in the summary.

#### 3.8.2 Adverse Events and Serious Adverse Events

Treatment-emergent adverse events (TEAEs) are defined as events present at baseline that worsen in intensity after administration of IP or events absent at baseline that emerge after administration of IP. IP TEAEs will be coded by MedDRA version 17.1 or more recent version and the type incidence, severity graded according to NCI CTCAE version 4.03, and relationship to IP will be summarized. Specific adverse events will be counted once for each subject for calculating percentages. In addition, if the same adverse event occurs multiple times within a particular subject, the highest severity and level of relationship observed will be reported. If any associations of interest between adverse events and baseline characteristics are observed, additional stratified results may be presented. All treatment-emergent adverse events will be summarized overall, as well as categorized by MedDRA System Organ Class and Preferred Term.

The AEs and SAEs occurring from the signing of the informed consent and prior to the initiation of study treatment will be listed.

## 3.8.3 Adverse Events of Special Interest

An adverse event of special interest (AESI) is one of scientific and medical interest specific to understanding of the IP and may require close monitoring and rapid communication by the investigator to the sponsor. A list of AESIs for this study can be found in the protocol. Other categories may be added or existing terms may be modified as necessary.

#### 3.8.4 Deaths and Treatment Discontinuations due to Adverse Events

For those subjects who died due to an AE, the AE contributing to death and the AE's relationship to IP will be summarized.

Summaries will be provided for TEAEs resulting in permanent discontinuation of IP. Supporting listings will be provided for AEs resulting in death and AEs resulting in permanent discontinuation of IP.

## 3.8.5 Clinical Laboratory Evaluation

Laboratory tests will be grouped according to chemistry, hematology, and urinalysis. Listings will be provided for all laboratory results, including urinalysis. For chemistry and hematology tests, the change in each laboratory parameter from baseline to each post-baseline visit will be summarized graphically.

For chemistry and hematology tests, laboratory abnormalities with toxicity grades according to the NCI CTCAE will be derived according to laboratory values. Laboratory abnormalities occurring from the start of IP administration to the last assessment on study will be presented. Tables will be generated showing the maximum toxicity grade, as well as any shifts of more than 2 grades from baseline to the maximum grade and to the last assessment on-study.

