## 3.8.5.1 Hepatic Function Abnormality (Hy's Law)

Hepatic function abnormality meeting the definition of Hy's law (ie, any increase in ALT or AST to greater than 3 × ULN and concurrent increase in total bilirubin to be greater than 2 × ULN) is considered an AESI and will be reported. Concurrent findings are those that derive from a single blood draw or from separate blood draws taken within 8 days of each other. Follow-up investigations and inquiries will be initiated promptly by the investigational site to determine whether the findings are reproducible and/or whether there is objective evidence that clearly supports causation by a disease (eg, cholelithiasis and bile duct obstruction with distended gallbladder) or an agent other than the investigational product.

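### The laboratory shift table shows only shifts of 3 or more grades, so worsening from Grade 1 to 3 or from Grade 2 to 4 is left out (minor)

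*SAP*

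**What the plan says.** SAP Section 3.8.5 derives grades for chemistry and hematology from the measured values: "laboratory abnormalities with toxicity grades according to the NCI CTCAE will be derived according to laboratory values". It does not print the grade scale or name a CTCAE version. The version appears in Section 3.8.2, for adverse events: "severity graded according to NCI CTCAE version 4.03".

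Two outputs by grade follow in one sentence of Section 3.8.5. The first is a worst-grade table: "Tables will be generated showing the maximum toxicity grade". The second is a shift table restricted to "any shifts of more than 2 grades from baseline to the maximum grade and to the last assessment on-study".

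The same section also plans listings ("Listings will be provided for all laboratory results, including urinalysis") and graphs ("the change in each laboratory parameter from baseline to each post-baseline visit will be summarized graphically"). The SAP plans no shift table with a lower threshold and no full cross-tabulation of baseline grade by worst grade.

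**The concern.** A shift table is there to tell worsening on treatment apart from an abnormality that the subject brought into the trial. A threshold of strictly more than 2 grades makes it blind to moves that most readers of a safety report would expect to see, such as Grade 1 at baseline to Grade 3 on treatment, or Grade 2 to Grade 4.

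What the table can show also depends on where the subject starts. The higher the baseline grade, the less room there is for a 3-grade rise, and from Grade 2 upward there is none. The subjects for whom a reference to baseline matters most, those already abnormal at entry, are therefore the ones it serves least.

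At stake is the clarity of one descriptive safety summary. Section 2.1.2 makes the description of safety and tolerability a secondary objective of the dose-expansion phase, so the table does serve a stated purpose.

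**Working it through.** The plan gives no figure to reproduce here, so the check is an enumeration of grade pairs.

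**Inputs**
- Threshold: a shift of more than 2 grades (Section 3.8.5).
- Grades derived from laboratory values (Section 3.8.5).
- Scale 0 to 4: assumed. A fatal grade cannot be read off a laboratory value, so Grade 5 is left out of the main count and checked separately.

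**Step 1: all upward shifts.** With 5 grades there are 5 × 4 / 2 = 10 upward pairs. A rise of d grades can occur in 5 − d ways.

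| Rise d | Pairs | Count | Shown under more than 2 | Shown under 2 or more |
|---|---|---|---|---|
| 1 | 0→1, 1→2, 2→3, 3→4 | 4 | no | no |
| 2 | 0→2, 1→3, 2→4 | 3 | no | yes |
| 3 | 0→3, 1→4 | 2 | yes | yes |
| 4 | 0→4 | 1 | yes | yes |

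- More than 2: 2 + 1 = 3 of 10.
- 2 or more: 3 + 2 + 1 = 6 of 10.

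**Step 2: by baseline grade.** The largest possible rise is 4 minus the baseline grade.
- Baseline 0: 4 grades, so it can qualify (0→3, 0→4).
- Baseline 1: 3 grades, so it can qualify only through 1→4.
- Baseline 2: 2 grades, so it can never qualify.
- Baseline 3: 1 grade, so it can never qualify.
- Baseline 4: none.

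**Step 3: worsening that ends at Grade 3 or 4.** There are 7 such pairs: 0→3, 1→3, 2→3, 0→4, 1→4, 2→4 and 3→4. The present rule shows 3 of them and omits 1→3, 2→3, 2→4 and 3→4. Under 2 or more, only 2→3 and 3→4 are still omitted.

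**Step 4: direction.** The sentence does not limit the shifts to worsening. Falls of 3 or more grades (3→0, 4→0, 4→1) would also qualify, so a subject starting at Grade 3 or 4 can appear, but only as an improvement. A subject starting at Grade 2 can move at most 2 grades either way and cannot appear at all.

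**Step 5: sensitivity to the scale.** If a Grade 5 were allowed, 2→5 would be the one worsening from Grade 2 able to enter the table. The pairs 1→3 and 2→4 are excluded on either scale.

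**Step 6: do the other outputs fill the gap?**
- Maximum-grade table: counts the subject at Grade 3 or 4, but the SAP mentions no baseline grade for it.
- Graphs: show change from baseline by parameter and visit, not by grade.
- Listings: hold both values for each subject, but give no count by treatment group.

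Each holds part of the information. None is a summary by grade that is referenced to baseline.

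**The case against.** The strongest reply is that nothing is hidden. A subject who goes from Grade 1 to 3 is counted at Grade 3 in the maximum-grade table, and the baseline value is in the listings. Worsening of a condition present at baseline also counts as treatment-emergent under Section 3.8.2, whatever the starting grade, so a laboratory abnormality reported as an adverse event is summarized there. The threshold contradicts no other section and drives no decision, and Section 1 leaves table templates to a programming plan that is not at hand. Most of this stands, and it is why the point is minor. It does not remove the point. The value-derived grades are a separate analysis from reported adverse events, not every laboratory shift need be reported as an event, and the threshold is fixed in the SAP itself.

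Three stronger readings are tempting, and the SAP supports none of them.
- *Liver risk is missed.* Section 3.8.5.1 reports Hy's law cases by multiples of the upper limit of normal ("any increase in ALT or AST to greater than 3 × ULN and concurrent increase in total bilirubin"). That reporting does not depend on the shift threshold, so the threshold cannot remove such a case.
- *The comparison between arms is distorted.* Safety in the expansion phase is descriptive, and no test of laboratory shifts between arms is planned. An imbalance in baseline grades is possible but hypothetical.
- *A given number of subjects is affected.* The SAP gives neither the distribution of baseline grades nor a rate of deterioration. A share of subjects starting at Grade 1 or 2 would be only those at risk of being left out, not those who worsen.

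**Conclusion.** The concern holds as a minor point about one safety table. As worded, the rule shows 3 of 10 upward shifts, against 6 under a threshold of 2 or more. It omits 1→3 and 2→4, and it can show no worsening from a baseline of Grade 2 or above. The counts rest on the plain meaning of *more than 2* and on an assumed 0 to 4 scale. The omission of 1→3 and 2→4 does not depend on the scale.

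The size is in grade pairs, not subjects, and the SAP does not allow a count of subjects. The loss is one cross-classification: for these subjects, no planned summary by grade tells on-treatment worsening from a pre-existing abnormality. The events themselves are still counted and listed.

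**What to change.** In Section 3.8.5, replace *more than 2 grades* with *2 or more grades*, keep both comparisons (baseline to maximum grade, and baseline to last on-study assessment), and state that the table is given by treatment group. This adds 0→2, 1→3 and 2→4.

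The new threshold would still leave out 2→3 and 3→4. A full cross-tabulation of baseline grade by worst on-treatment grade, per parameter and treatment group, would show both and make the choice of threshold unnecessary. State the grade scale and the CTCAE version for laboratory values in the same edit.

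The cost is one change to the SAP text and to the table program. No new data are needed. The downside is a longer table.

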## 3.8.5.1 Hepatic Function Abnormality (Hy's Law)

Hepatic function abnormality meeting the definition of Hy's law (ie, any increase in ALT or AST to greater than 3 × ULN and concurrent increase in total bilirubin to be greater than 2 × ULN) is considered an AESI and will be reported. Concurrent findings are those that derive from a single blood draw or from separate blood draws taken within 8 days of each other. Follow-up investigations and inquiries will be initiated promptly by the investigational site to determine whether the findings are reproducible and/or whether there is objective evidence that clearly supports causation by a disease (eg, cholelithiasis and bile duct obstruction with distended gallbladder) or an agent other than the investigational product.

## 3.8.6 Other Safety Evaluations

## 3.8.6.1 Vital Signs

Vital signs will be assessed at baseline and throughout the study. Vital signs will be summarized graphically to illustrate changes from baseline.

#### 3.8.6.2 Electrocardiogram (ECG)

Electrocardiogram (ECG) parameters will be assessed at baseline as well as throughout the study. Absolute values and maximum changes from baseline to post-therapy in QTc will be summarized using descriptive statistics.

#### 3.8.6.3 ECOG Performance Status

Eastern Cooperative Oncology Group (ECOG) performance status will be assessed at baseline as well as throughout the study. ECOG will be summarized by study visit and will include descriptive statistics for the value of the parameters and the changes from baseline.

## 3.9 Immunogenicity

Analyses to assess the immunogenic potential of durvalumab (MEDI4736) will be performed by the MedImmune Global Pharmacokinetics - Pharmacodynamics (PK-PD) & Bioanalysis group or designee.

#### 3.10 Pharmacokinetics

Pharmacokinetic data analyses will be performed by the MedImmune Global PK-PD & Bioanalysis group or designee.

## 4 INTERIM ANALYSIS

Interim futility analyses for MEDI0680/durvalumab combination vs nivolumab will be performed in a continuous manner using Bayesian predictive probability. Bayesian predictive probability is used in the setting of single-arm trials with tumor response endpoints such as OR and allows for continuous assessments for early Go/NoGo decision making (Lee and Liu, 2008). A joint Bayesian predictive probability approach has been developed which allows for continuous assessments of the delta  $(\delta)$ , or difference, of the ORRs between MEDI0680/durvalumab combination and nivolumab.

The interim analyses will begin after 20 subjects in the MEDI0680/durvalumab combination have been randomized and have reached their second post-baseline disease assessment or have completed study, whichever occurs first. Subject accrual may be paused in both treatment groups for the first interim analyses; however, an accrual pause may not be necessary if existing data upon enrollment of 20 subjects in the MEDI0680/durvalumab combination suggest futility criteria have not been triggered as per the predefined futility stopping criteria defined below. If futility is not triggered, further enrollment will continue without pause and continuous monitoring for futility will commence after an additional 4 subjects reach their second post-baseline disease assessment or completes the study, whichever occurs first, until enrollment is complete.

Given the existing observed data during the continuous monitoring stage, the joint predictive probability is obtained by calculating the probability of reaching a NoGo decision should the treatment groups be enrolled and evaluated to the maximum planned final sample size of 60 (40 in MEDI0680/durvalumab combination and 20 in nivolumab). Further enrollment into both treatment groups will be terminated due to futility if there is a high probability of reaching a NoGo decision upon enrollment of 60 subjects given the existing observed data (ie, predictive probability of a NoGo decision > 90%). An efficacy decision would be

reached if there is a high probability of reaching a Go decision upon enrollment of 60 subjects given the existing observed data (ie, predictive probability of a Go decision > 90%). If an efficacy decision is reached, enrollment may continue, but planning activities for further development of the MEDI0680/durvalumab combination may be triggered.

Decision matrices for continuous monitoring of ORR  $\delta$  at the prespecified MEDI0680/durvalumab combination sample sizes for interim futility assessments are presented in Figure 4-1. The matrices presented are examples and assume that the MEDI0680/durvalumab combination treatment group will randomize in a 2:1 ratio to the nivolumab treatment group. Additional decision matrices will be prepared as needed to accommodate observed data. Futility, continuation, and efficacy decisions are marked using red, yellow, and green cells, respectively, and allow for an evaluation of varying combinations of responses between the two treatment groups. The target  $\delta$  was set so as to demonstrate a 20% increase in the MEDI0680/durvalumab combination ORR over the benchmark nivolumab ORR based on investigator assessments, in a similar RCC population (ORR = 25.1 [95% CI: 21.0%, 29.6%]; Motzer et al, 2015). Given assumptions of a benchmark ORR in the nivolumab treatment group of 25% and a true  $\delta$  = 20%, darker color cells represent scenarios that would be observed in practice with a 95% likelihood.

For example, given a target  $\delta$  of 20% and assuming 3 observed responders in the nivolumab treatment group after 10 subjects have reached their second post-baseline disease assessment or have completed the study, observing 4 or fewer responders after 20 subjects in the MEDI0680/durvalumab combination have reached their second post-baseline disease assessment or have completed the study would trigger stopping enrollment claiming futility due to a high probability of reaching a NoGo decision upon enrollment to 60 subjects given the existing observed data Figure 4-2flo and Table 4.1).

A false negative is defined as observing either futility criteria during the continuous monitoring stage or NoGo criteria upon enrollment of 60 subjects in a given treatment group when the true ORR  $\delta$  is greater than or equal to the target  $\delta$  (ie, False Negative: P[NoGo Decision | True  $\delta \geq$  Target]). Assuming a true  $\delta$  of 20%, the false negative rate is 11% (see highlighted cell in Table 4.1 below). Assuming a true  $\delta$  of 25%, the false negative rate is 5%. Additionally, assuming a true  $\delta$  of 20%, the Go decision rate (efficacy decision during the continuous monitoring stage or a Go decision upon enrollment of 60 subjects) is 37% with confirmation at the final analysis 75%.

Upon enrollment of 60 subjects in the dose-expansion phase, a final analysis will be performed. NoGo criteria will be met if the probability that the  $\delta$  exceeds the pre-specified

[figure not shown]
target of 20% is less than 10% (ie, NoGo:  $P[\delta > Target] < 10\%$ ). Go criteria will be met if the probability that the  $\delta$  exceeds the pre-specified target of 20% is more than 70% (ie, Go:  $P[\delta > Target] > 70\%$ ). For futility analyses, a response is defined as either a confirmed or unconfirmed CR or PR as per RECIST 1.1 and for the final analysis a response is defined as a confirmed CR or PR as per RECIST 1.1.

At interim analyses, efficacy and selected safety data will be summarized to assess the overall benefit-risk profile. The analysis populations to be used for the interim analysis are described below:

- As-treated with 17 weeks of potential follow up is defined as all subjects in the Astreated Population who have a baseline disease assessment and have an opportunity to be followed for at least 17 weeks (i.e., received the first dose of MEDI0680, durvalumab or nivolumab, whichever earliest, at least 17 weeks ago). The 17 weeks are to have at least 2 post-baseline disease assessments plus the one week visit window. This is the primary analysis population for the interim analysis of efficacy data.
- Response evaluable with 17 weeks of potential follow up is defined as all subjects in the As-treated Population who 1) have a baseline disease assessment; 2) have an opportunity to be followed for at least 17 weeks; and 3) have any post-baseline disease assessments or experience clinical PD/death. This is the secondary analysis population for the interim analysis of efficacy data.
- As-treated with 9 weeks of potential follow up is defined as all subjects in the Astreated Population who have a baseline disease assessment and have had an opportunity to be followed for at least 9 weeks. The 9 weeks are to have at least 1 post-baseline disease assessments plus one week visit window. This is the exploratory analysis population for the interim analysis of efficacy data.
- **As-treated Population**, as defined in section 3.2, is the primary analysis population for the interim analysis of safety data.

Figure 4-1 Decision Matrices for Continuous Monitoring

(MEDI0680 + Durvlumab vs Nivolumab: 10% false negative if effect = 20%)

[figure not shown]
[figure not shown]

Figure 4-2 Visual Joint Predictive Probability Operating Characteristics

[figure not shown]

Table 4.1 Joint Predictive Probability Operating Characteristics

| True Effect
Size |     |      |          | Decision based on Continuous Assessments    |          |   |  |
|---------------------|-----|------|----------|---|----------|---|--|
| (Benchmark = 25%)   | Go  | NoGo | Consider | Efficacy
(% confirmed
with the final) | Futility | Expected Sample Size up to a decision being made (% decision making prior to final) | Expected Sample Size stopping for futility only (% interim stopping) |
| 0%                  | 1%  | 77%  | 23%      | 1% (28%)                                    | 82%      | 40 (78%)  | 41 (77%)   |
| 15%                 | 13% | 17%  | 70%      | 20% (65%)                                   | 24%      | 51 (39%)  | 55 ( 20% )  |
| 20%                 | 28% | 7%   | 65%      | 37% (75%)                                   | 11%      | 50 (43%)  | 58 (9%)  |
| 25%                 | 47% | 2%   | 51%      | 56% (84%)                                   | 5%       | 47 (56%)  | 59 ( 3% )   |
| 30%                 | 67% | 1%   | 32%      | 74% (90%)                                   | 2%       | 43 (72%)  | 60 (1%)  |

Abbreviations: PP: Predictive Probability. Target  $\delta = 20\%$ ; Go: Pr( $\delta > 20\%$ ) > 70%; NoGo: Pr( $\delta > 20\%$ ) < 10%; Efficacy: PP(Go) > 90%); Futility: PP(NoGo) > 90%).

